5.2.3.2 Formulation/ Preparation

MK-3475 is provided as a liquid solution (100 mg/vial) in Type I glass vials intended for single use only. The drug product is stored as a stable liquid solution under refrigerated conditions (2°C-8°C). The liquid product is intended for IV administration. The liquid drug product can be further diluted with normal saline in IV containers made of polyvinyl chloride (PVC) or non-PVC material. The infusion solution should be immediately administered. If not used immediately, vials and/or IV bags may be stored at 2-8°C for up to a cumulative time of 20 hours. If refrigerated, the vials and/or IV bags should be allowed to equilibrate to room temperature prior to subsequent use. MK-3475 solutions may be stored at room temperature for a cumulative time of up to 6 hours. This includes room temperature storage of reconstituted drug product solution and liquid drug product in vials, room temperature storage of infusion solution in the IV bag and the duration of infusion.

Please see the Investigators Brochure for additional drug formulation information.

5.2.3.3 Dose Modification (Escalation/Titration/Other)

Adverse events (both non-serious and serious) associated with pembrolizumab exposure may represent an immunologic etiology. These adverse events may occur shortly after the first dose or several months after the last dose of treatment. Pembrolizumab must be withheld for drug-related toxicities and severe or life-threatening AEs as per Table 3 below. See Section 5.4.1 for supportive care guidelines, including use of corticosteroids.

Table 3

Dose Modification Guidelines for Drug-Related Adverse Events

Toxicity	Hold Treatment For Grade	Timing for Restarting Treatment	Treatment Discontinuation
Diarrhea/Colitis	2-3	Toxicity resolves to Grade 0-1	Toxicity does not resolve within 12 weeks of last dose or inability to reduce corticosteroid to 10 mg or less of prednisone or equivalent per day within 12 weeks
	4	Permanently discontinue	Permanently discontinue
AST, ALT, or Increased Bilirubin	2	Toxicity resolves to Grade 0-1	Toxicity does not resolve within 12 weeks of last dose
	3-4	Permanently discontinue (see exception below) ^a	Permanently discontinue
Type 1 diabetes mellitus (if new onset) or Hyperglycemia	T1DM or 3-4	Hold pembrolizumab for new onset Type 1 diabetes mellitus or Grade 3-4 hyperglycemia associated with evidence of beta cell failure	Resume pembrolizumab when patients are clinically and metabolically stable
Hypophysitis	2-4	Toxicity resolves to Grade 0-1. Therapy with pembrolizumab can be continued while endocrine replacement therapy is instituted	Toxicity does not resolve within 12 weeks of last dose or inability to reduce corticosteroid to 10 mg or less of prednisone or equivalent per day within 12 weeks
Hyperthyroidism	3	Toxicity resolves to Grade 0-1	Toxicity does not resolve within 12 weeks of last dose or inability to reduce corticosteroid to 10 mg or less of prednisone or equivalent per day within 12 weeks
	4	Permanently discontinue	Permanently discontinue
Hypothyroidism		Therapy with pembrolizumab can be continued while thyroid replacement therapy is instituted	Therapy with pembrolizumab can be continued while thyroid replacement therapy is instituted
Infusion Reaction	2 ^b	Toxicity resolves to Grade 0-1	Permanently discontinue if toxicity develops despite adequate premedication
	3-4	Permanently discontinue	Permanently discontinue
Pneumonitis	2	Toxicity resolves to Grade 0-1	Toxicity does not resolve within 12 weeks of last dose or inability to reduce corticosteroid to 10 mg or less of prednisone or equivalent per day within 12 weeks
	3-4	Permanently discontinue	Permanently discontinue
Renal Failure or Nephritis	2	Toxicity resolves to Grade 0-1	Toxicity does not resolve within 12 weeks of last dose or inability to reduce corticosteroid to 10 mg or less of prednisone or equivalent per day within 12 weeks
	3-4	Permanently discontinue	Permanently discontinue
All Other Drug-Related Toxicity ^c	3 or Severe	Toxicity resolves to Grade 0-1	Toxicity does not resolve within 12 weeks of last dose or inability to reduce corticosteroid to 10 mg or less of prednisone or equivalent per day within 12 weeks
	4	Permanently discontinue	Permanently discontinue

Note: Permanently discontinue for any severe or Grade 3 drug-related AE that recurs or any life-threatening event.

^a For patients with liver metastasis who begin treatment with Grade 2 AST or ALT, if AST or ALT increases by greater than or equal to 50% relative to baseline and lasts for at least 1 week then patients should be discontinued.

^b If symptoms resolve within one hour of stopping drug infusion, the infusion may be restarted at 50% of the original infusion rate (e.g., from 100 mL/hr to 50 mL/hr). Otherwise dosing will be held until symptoms resolve and the subject should be premedicated for the next scheduled dose; Refer to **Error! Reference source not found.** – Infusion Treatment Guidelines for further management details.

^c Patients with intolerable or persistent Grade 2 drug-related AE may hold study medication at physician discretion. Permanently discontinue study drug for persistent Grade 2 adverse reactions for which treatment with study drug has been held, that do not recover to Grade 0-1 within 12 weeks of the last dose.

Dosing interruptions are permitted in the case of medical/surgical events or logistical reasons not related to study therapy (e.g., elective surgery, unrelated medical events, patient vacation, and/or holidays). Subjects should be placed back on study therapy within 3 weeks of the

scheduled interruption, unless otherwise discussed with the Sponsor. The reason for interruption should be documented in the patient's study record.

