9.1.4 Evaluating Adverse Events

An Investigator who is a qualified physician will evaluate all adverse events according to the NCI Common Terminology for Adverse Events (CTCAE), version 4.0. Any adverse event which changes CTCAE grade over the course of a given episode will have each change of grade recorded on the adverse event case report forms/worksheets.

All adverse events regardless of CTCAE grade must also be evaluated for seriousness.

Remainder of Page Intentionally Left Blank

Table 8: Evaluating Adverse Events

An Investigator who is a qualified physician will evaluate all adverse events as to:

V4.0 CTCAE Grading	Grade 1	Mild; asymptomatic or mild symptoms; clinical or diagnostic observations only; intervention not indicated.
	Grade 2	Moderate; minimal, local or noninvasive intervention indicated; limiting age-appropriate instrumental ADL.
	Grade 3	Severe or medically significant but not immediately life-threatening; hospitalization or prolongation or hospitalization indicated; disabling; limiting self-care ADL.
	Grade 4	Life threatening consequences; urgent intervention indicated.
	Grade 5	Death related to AE
Seriousness	A serious adverse event is any adverse event occurring while the subject is enrolled into the study:	
	† Results in death ; or	
	† Is life threatening ; or places the subject, in the view of the investigator, at immediate risk of death from the event as it occurred (Note: This does not include an adverse event that, had it occurred in a more severe form, might have caused death.); or	
	† Results in a persistent or significant disability/incapacity (substantial disruption of one’s ability to conduct normal life functions); or	
	† Results in or prolongs an existing inpatient hospitalization (hospitalization is defined as an inpatient admission, regardless of length of stay, even if the hospitalization is a precautionary measure for continued observation. (Note: Hospitalization for an elective procedure to treat a pre-existing condition that has not worsened is not a serious adverse event. A pre-existing condition is a clinical condition that is diagnosed prior to the use of a Merck product and is documented in the patient’s medical history.); or	
	† Is a congenital anomaly/birth defect (in offspring of subject taking the product regardless of time to diagnosis); or	

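### For Grade 4 hypophysitis and Grade 4 hyperglycemia, the note under Table 3 and the table's own rows give different MK-3475 instructions

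*Combined protocol and SAP*

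**What the plan says.** Section 5.2.3.3 makes the table binding: "Pembrolizumab must be withheld for drug-related toxicities and severe or life-threatening AEs as per Table 3 below". Table 3 then gives, for each toxicity, the grades that trigger a hold, the restart condition and the discontinuation condition. A general note below it reads: "Permanently discontinue for any severe or Grade 3 drug-related AE that recurs or any life-threatening event".

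Two rows treat Grade 4 as a hold:

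- **Hypophysitis.** The hold column lists Grades 2-4 with no separate Grade 4 line. The restart cell reads "Toxicity resolves to Grade 0-1. Therapy with pembrolizumab can be continued while endocrine replacement therapy is instituted". The discontinuation cell covers only failure to resolve, or failure to reduce steroids, within 12 weeks.
- **New-onset type 1 diabetes or hyperglycemia.** The hold column lists type 1 diabetes or Grades 3-4. The restart column says "Hold pembrolizumab for new onset Type 1 diabetes mellitus or Grade 3-4 hyperglycemia associated with evidence of beta cell failure". The discontinuation column says "Resume pembrolizumab when patients are clinically and metabolically stable".

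Table 8 in Section 9.1.4 describes CTCAE Grade 4 as "Life threatening consequences; urgent intervention indicated".

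**The concern.** If Grade 4 means life-threatening, as Table 8 says, the note permanently ends MK-3475 for any Grade 4 event, while these two rows allow the same patient to be re-dosed. The document does not say whether the note or the row prevails. This is a multicenter trial with safety as its primary objective, so one event could be handled in opposite ways at two sites that both follow the protocol. That bears on the patient's safety, and on how exposure and discontinuations are recorded and compared across 15 subjects.

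Two smaller defects sit in the same rows. The diabetes row's discontinuation cell contains a resume instruction and no discontinuation condition. The hypophysitis restart cell combines a resolution condition with a sentence allowing therapy to continue, without saying whether that sentence applies during the hold or after it.

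**Working it through.** The plan states no figure on this point, so there is none to reproduce. The check compares the texts and then applies the escalation rule.

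**Step 1: note against rows at Grade 4.** Table 3 has ten toxicity rows. Hypothyroidism lists no grade. The other nine list Grade 4:

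- Seven end MK-3475 permanently at Grade 4, in line with the note: diarrhea/colitis, AST/ALT/bilirubin (with a footnoted exception), hyperthyroidism, infusion reaction, pneumonitis, renal failure or nephritis, and all other drug-related toxicity.
- Two hold and restart at Grade 4: hypophysitis and diabetes/hyperglycemia.

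The AST/ALT/bilirubin row points to its exception explicitly. The two endocrine rows have no such pointer, so the text does not show that they are intended exceptions.

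**Step 2: do other sections settle it?**

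- Section 5.8 suspends accrual for review after any Grade 4 toxicity. That acts on enrollment and does not say whether the affected patient may be re-dosed.
- Section 5.2.4 removes a patient from the trial after a toxicity hold of more than 2 weeks. Section 5.2.5 ends investigational treatment after a hold of more than 63 days. Neither covers a shorter hold.
- Sections 5.2.1.1.3 and 5.3.2 require stopping BCG, withdrawal, or both when steroids are given for an immune event of Grade 3 or higher. They leave MK-3475 open if the patient is not withdrawn.

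**Step 3: effect on the escalation count.** Sections 5.2.3.1, 5.8, 6.1 and 8.1.6.2.1 count a subject whose MK-3475 is either held or stopped. For one Grade 4 event:

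- following the note (stop): count = 1
- following the row (hold): count = 1
- difference: 1 - 1 = 0

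The Grade 4 conflict therefore cannot move the escalation decision.

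**Step 4: the hypophysitis wording.** If the continuation sentence meant no interruption at all, the case would not be counted:

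| Situation | Held or stopped | Not interrupted |
|---|---|---|
| Only event in first 3 | 1/3: expand to 6 | 0/3: escalation open |
| One other counted event in first 3 | 2/3: no escalation | 1/3: expand to 6 |
| 1/3 already counted, case in subjects 4-6 | 2/6: no escalation | 1/6: escalation open |

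To size this, let p be the per-subject chance of any other held or stopped dose and q the added chance of hypophysitis. The documents give neither, so both are assumptions. With p* the chance that a subject is counted:

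P(escalation open) = (1-p*)^3 + 3p*(1-p*)^2 × (1-p*)^3

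If hypophysitis is not counted, p* = p. If it is counted, p* = 1-(1-p)(1-q).

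| p | Not counted | Counted, q = 1% | Counted, q = 5% |
|---|---|---|---|
| 0.10 | 0.906 | 0.891 | 0.824 |
| 0.20 | 0.709 | 0.691 | 0.622 |
| 0.30 | 0.494 | 0.480 | 0.425 |

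The difference runs from 0.494 - 0.480 = 0.014 to 0.709 - 0.622 = 0.087. It exists only on the no-interruption reading.

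**The case against.** **The rows may be deliberate exceptions.** A specific row can be read as overriding a general note, and endocrine events managed by replacement are a plausible place for that. The document does not say so, however, and it does mark the one exception it makes elsewhere in the table.

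**Grade 4 and life-threatening may not coincide.** The note does not name a grade, and Table 8 separately defines a life-threatening serious event as immediate risk of death in the investigator's view. On that definition some Grade 4 laboratory values would fall outside the note. This stands as a possible reading, but Table 8 also describes Grade 4 itself in life-threatening terms, so a site cannot tell which meaning applies.

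**A reader might infer that the hypophysitis row gives opposite instructions and so can decide whether 200 mg is studied.** The documents do not support that. The continuation sentence sits in the restart column directly after the resolution condition, and the hold column lists Grades 2-4. Section 5.4.1 places hormone replacement during the steroid taper, which starts once symptoms reach Grade 1 or less. The natural reading is hold, then restart while replacement goes on, and every such case is counted. The hypothyroidism row does use similar words, "Therapy with pembrolizumab can be continued while thyroid replacement therapy is instituted", to mean no interruption, but its hold cell is blank. What remains is an ambiguity. Escalation is also a determination by the Data Safety Review Team and is not automatic.

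**The misplaced diabetes text may be a layout slip.** The hold and resume instructions are clear wherever they sit. Even so, the row states no discontinuation condition; only Sections 5.2.4 and 5.2.5 limit the length of a hold.

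**Conclusion.** The conflict between the note and the two endocrine rows is real and stands in the current text. It covers two of the nine rows that list Grade 4, and for each the choice is between a permanent stop and hold-then-restart. The conclusion rests on Table 8's description of Grade 4 and on the lack of any statement about which text prevails. The consequence is inconsistent handling and recording of individual patients. It has no effect on the escalation count.

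The hypophysitis wording is a secondary ambiguity. It could leave a case uncounted only on the less likely reading; there the illustrative change in the chance that escalation stays open is about 0.01 to 0.09, under assumed rates that the documents do not supply. The point deserves correction as a matter of internal consistency. It does not show a flaw in the escalation design.

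**What to change.** In Table 3:

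1. Reconcile the note with the hypophysitis and diabetes/hyperglycemia rows so that each Grade 4 event has one instruction, either by making the rows follow the note or by naming them as exceptions to it.
2. State whether the hypophysitis continuation sentence applies during the hold or after it.
3. Make the diabetes/hyperglycemia discontinuation cell fit its column, and make it consistent with the limits on hold length in Sections 5.2.4 and 5.2.5.

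The sponsor's safety team decides the clinical content; this review takes no position on which instruction is right. The cost is a correction to one table in a protocol amendment, with no added patients, visits or procedures.

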5.2.4 Schedule Modification for Combination Therapy

The dosing schedule of the combination therapy will not be altered except on an individual drug basis (such as holding either individual BCG or MK-3475 therapy) if the time period is for 2 weeks or less. That is to say holding either of the two medications included in the combination therapy for less than two weeks should not affect the dosage schedule for the other medication. Patients will be discontinued from the trial if one of the two medications is held for more than 2 weeks because of toxicity. BCG treatment may continue, after a 2 week hold, outside of the study at the discretion of the treating Investigator.

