5.2 Trial Treatments

The treatments to be used in this trial are outlined below in **Table 2**.

Table 2: Trial Treatment

Drug	Dose/Potency	Dose Frequency	Route of Administration	Regimen/Treatment Period	Use
MK-3475 ^{a, b}	100 mg	Every 21 days	IV infusion	6 cycles	Experimental
MK-3475 ^b	200 mg	Every 21 days	IV infusion	6 cycles	Experimental
BCG	1 vial	Every 7 days	Bladder Instillation	6 cycles	Approved

^aThe first 3 subjects will be dosed at 100 mg. If the Data Safety Review Team approves, the dose will be escalated to 200 mg with the fourth subject enrolled.

^bThe MK-3475 dosing interval may be increased due to toxicity as described in Section 5.2.3.3. BCG treatment may be interrupted or delayed as per the instructions for use supplied with BCG (Section 5.2.1.1.3).

BCG: One vial of BCG suspended in 50 ml preservative-free saline. BCG is to be given through a urinary catheter (intravesically) into the bladder. BCG treatment will occur once per week for 6 weeks. BCG treatment will commence on the 3rd cycle of treatment with MK-3475, Week 7. BCG is a FDA approved treatment and will be supplied commercially through the study site pharmacy.

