5.2.5 Timing of Dose Administration

Trial MK-3475 treatment (100 or 200 mg fixed dose) should be administered on Day 1 of each cycle after all procedures/assessments have been completed as detailed on the Trial Flow Chart (Section 7.0). MK-3475 treatment may be administered up to 3 days before or after the scheduled Day 1 of each cycle due to administrative reasons. Subjects may be dosed no less than 18 days from the previous dose. If treatment is held for greater than 3 cycles (or 63 days) subject will be withdrawn from investigational product treatment permanently.

All trial treatments will be administered on an outpatient basis unless the patient is currently admitted to the hospital for another purpose which does not exclude treatment with BCG or MK-3475 or enrollment into the study.

MK-3475 will be administered as a 30 minute IV infusion (treatment cycle intervals may be increased due to toxicity as described in Section 5.2.3.3). Sites should make every effort to target infusion timing to be as close to 30 minutes as possible. However, given the variability of infusion pumps from site to site, a window of -5 minutes and +10 minutes is permitted (i.e., infusion time is 30 minutes: -5 min/+10 min).

The Procedure Manual contains specific instructions for MK-3475 dose calculation, reconstitution, preparation of the infusion fluid, and administration.

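### Section 5.2.4 takes a subject off the trial after a toxicity hold of more than 2 weeks, Table 3 lets MK-3475 restart on recovery (with a 12-week limit in 7 of 9 rows), and no text says which governs

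*Combined protocol and SAP*

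**What the plan says.** Three places in the protocol set limits on holding MK-3475 for toxicity, or on holding it at all.

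- **Section 5.2.4** covers a hold of either BCG or MK-3475: "Patients will be discontinued from the trial if one of the two medications is held for more than 2 weeks because of toxicity". The consequence is the end of trial participation.
- **Section 5.2.3.3, Table 3** gives the usual restart condition as "Toxicity resolves to Grade 0-1". The usual ground for discontinuation is "Toxicity does not resolve within 12 weeks of last dose". Footnote c applies the same limit to persistent Grade 2 events "that do not recover to Grade 0-1 within 12 weeks of the last dose". The row for type 1 diabetes and hyperglycemia has no time limit: "Resume pembrolizumab when patients are clinically and metabolically stable". The consequence is the end of study drug.
- **Section 5.2.5** adds: "If treatment is held for greater than 3 cycles (or 63 days) subject will be withdrawn from investigational product treatment permanently". This limit is not confined to toxicity, and it too ends study drug only.

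Two cross-references send toxicity delays to Table 3's section. Table 2 footnote b says "MK-3475 dosing interval may be increased due to toxicity as described in Section 5.2.3.3", and Section 5.2.5 says "treatment cycle intervals may be increased due to toxicity as described in Section 5.2.3.3". Neither mentions 5.2.4, and 5.2.4 cites neither Table 3 nor 5.2.5. The list of mandatory reasons for stopping treatment in 8.1.5.1 does not mention length of hold.

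For BCG, Sections 5.2.1.1.3 and 5.3.2 also use 2 weeks when the delay is due to steroids for a grade 1 or 2 immune event. Beyond that, they let the Investigator choose between stopping BCG alone and withdrawing the subject.

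**The concern.** For one and the same MK-3475 hold, 5.2.4 requires that the subject leave the trial and Table 3 permits re-dosing. Both are current text, and a site can find support for either. The trial is multicenter, plans 15 subjects and has the safety of the combination as its primary objective. If sites follow different sections, whether a subject is re-exposed to MK-3475 after a toxicity depends on the site. The exposure behind the adverse event proportions in Section 10 would then not be governed by one rule.

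The consequences differ as well as the time limits. Leaving the trial and stopping study drug are different events, and the protocol does not say whether a subject removed under 5.2.4 enters the follow-up described in 8.1.6.6.

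**Working it through.** The plan states no figure for this point, so there is none to reproduce. The check is a row count and a common time scale.

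**1. Table 3 rows in which MK-3475 is held and may restart**

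| Row | 12-week resolution limit | Steroid criterion added |
|---|---|---|
| Diarrhea/colitis, Grade 2-3 | yes | yes |
| AST, ALT or bilirubin, Grade 2 | yes | no |
| Type 1 diabetes/hyperglycemia | none | no |
| Hypophysitis, Grade 2-4 | yes | yes |
| Hyperthyroidism, Grade 3 | yes | yes |
| Infusion reaction, Grade 2 | none | no |
| Pneumonitis, Grade 2 | yes | yes |
| Renal failure/nephritis, Grade 2 | yes | yes |
| All other, Grade 3 or severe | yes | yes |

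The total is 9 rows: 7 with the 12-week limit, 6 of these with the steroid criterion, and 2 with no time limit. The hypothyroidism row has no hold.

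**2. Time scale**

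Inputs: 21-day cycle (Table 2); 2 weeks = 14 days (5.2.4); 12 weeks from the last dose = 12 × 7 = 84 days (Table 3); 63 days (5.2.5). The last dose is day 0 and the next is due on day 21. The protocol does not define the start of a hold, so both counts are shown.

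| | Hold counted from missed dose | Hold counted from last dose |
|---|---|---|
| 5.2.4 limit reached | 21 + 14 = day 35 | day 14 |
| Table 3 deadline for recovery | day 84 | day 84 |
| Recovery days in conflict | 36 to 84: 84 − 35 = 49 days | 15 to 84: 84 − 14 = 70 days |
| 5.2.5 limit reached | 21 + 63 = day 84 | day 63 |

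The second count is an outer figure, because day 14 falls before the next dose is due. On the first count the 5.2.5 limit falls on the same day as the Table 3 deadline. It allows holds of 15 to 63 days, but only by implication. The Table 3 date is a deadline for recovery, and the table sets no last date for re-dosing.

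**3. Doses affected**

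MK-3475 is given at Weeks 1, 4, 7, 10, 13 and 16 (flow chart). A hold at Week 7 leaves 4 of 6 doses depending on which section is followed, and a hold at Week 10 leaves 3 of 6. Each is one fewer if the missed dose is skipped, which the protocol does not say.

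**4. BCG**

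Sections 5.2.4, 5.2.1.1.3 and 5.3.2 agree on 2 weeks and differ only in consequence. Section 5.4.1 suggests a steroid taper of at least 4 weeks (28 days) for several Grade 2 immune events. If a taper starts on the day of an instillation and another is due 7 days later, the delay is at least 28 − 7 = 21 days, against a limit of 14. A later start within that week makes the delay longer. The limit is therefore exceeded when the taper starts before the sixth instillation. A taper starting at or after the Week 12 instillation delays no BCG.

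**The case against.** The strongest reply is that 5.2.4 is a special rule for the combination. Its heading and wording concern combination therapy, and 8.1.2 separates two cycles of MK-3475 alone, concurrent treatment in cycles 3 and 4, and two further single-agent cycles. If 5.2.4 governs only the overlap, the 12-week limits keep their effect in 4 of 6 cycles. This reading is reasonable and would narrow the problem. But the text does not state that scope, and within cycles 3 and 4 the two rules would still give opposite instructions.

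A second reply is that 5.2.4 is simply the stricter limit and overrides. That removes the clash, but leaves the 12-week limits without effect for these holds. It also fits poorly with the two cross-references that send toxicity delays to 5.2.3.3.

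It is also fair that not every row is equally likely to produce a long hold. Section 5.4.1 says infusion reactions generally resolve within 24 hours, and the hypophysitis row lets therapy continue during hormone replacement. The row count shows how far the texts conflict, not how often it will happen.

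A reader might infer more than the documents support:

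- *That Table 3 allows a 12-week hold.* The 12 weeks run from the last dose, which is 84 − 21 = 63 days past the due date.
- *That the escalation count or the response denominator changes.* The escalation rule counts any dose withheld or discontinued for toxicity, and 5.7 places enrolled subjects in an intent-to-treat population.
- *That response data are lost.* Section 8.1.5.1 requires an off-study visit and a 30-day safety visit but does not say that later follow-up ends. Section 8.1.6.6 already covers subjects who stop treatment without progression, and flow chart footnote g allows chart review.
- *That a taper during the BCG weeks always breaks the 2-week limit.* It does not once the last instillation has been given, and the 5.4.1 measures are suggestions.

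**Conclusion.** The point holds for MK-3475 toxicity holds. Section 5.2.4 and Table 3 give opposite instructions for a subject who recovers after the 2-week limit but within 12 weeks of the last dose, and no text sets precedence. The span is 49 days (days 36 to 84) if the hold runs from the missed dose, and 70 days (days 15 to 84) if it runs from the last dose. If 5.2.4 covers only the BCG overlap, the conflict is confined to holds in cycles 3 and 4 but does not disappear. The consequences also differ: off the trial under 5.2.4, off study drug under Table 3 and 5.2.5.

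The BCG strand is secondary. The time limit is the same throughout; what is missing is a statement that the Investigator's option to stop BCG alone is an exception to 5.2.4.

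This should be fixed because two instructions on re-exposure after toxicity cannot both be followed. The case rests on that and on possible differences between sites, not on any demonstrated bias in an analysis. The documents give no expected frequency of long holds, so the number of subjects affected cannot be estimated.

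**What to change.** Reconcile 5.2.4, Table 3 and 5.2.5 and, for BCG, 5.2.1.1.3 and 5.3.2 in one amendment. It should state:

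- which section governs toxicity holds of each drug, and in which cycles;
- from what date a hold is counted;
- whether exceeding the limit ends that drug, all study treatment or trial participation;
- whether the steroid-delay rule for BCG is an exception to 5.2.4;
- whether a subject discontinued under 5.2.4 falls under the follow-up in 8.1.6.6.

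Then check the result against the taper text in 5.4.1. Which limit applies is for the sponsor's clinicians to decide. The cost is amendment wording, with no additional patients; any follow-up retained uses visits already in the flow chart.
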